### 9.3.3 Covariables

The key covariables described for both the Moderna vaccination targeting SARS-CoV-2-exposed case-cohort and the myocarditis cohort will include variables that include information from one year or two years before until the day of Moderna vaccination (in the case-cohort design) or until the day of myocarditis/pericarditis onset (in the cohort design), such as the following, depending on what the different DAPs have collected: country of residence, calendar time, age, sex, selected comorbidities (e.g., diabetes mellitus, hypertension, obesity, cerebrovascular disease, cardiac history, chronic lung disease, chronic kidney disease, chronic liver disease, history of cardiac inflammation, autoimmune disorders, immunocompromise, substance use disorders, history of cancer), Charlson Comorbidity Index (CCI), relevant medical treatments (e.g., chemotherapy or

radiation for cancer, systemic immunomodulator therapy, immunosuppression, plasmapheresis, intravenous immunoglobulins (IVIG), systemic steroids, cardiotoxic medications), history of COVID-19 infection, other vaccinations targeting SARS-CoV-2, and other vaccinations (e.g., influenza, hepatitis B). Health care utilisation will be measured by the frequency of inpatient, outpatient, intensive care unit (ICU), emergency room (ER), and primary-care encounters. For the Moderna vaccination targeting SARS-CoV-2, characteristics of utilization will be described, including doses received, formulation (if additional options become available during the study period). As available, lifestyle factors such as smoking status, activity level, and other factors may be assessed.

It may be possible that not all information is available for each DAP, and some data may need to be searched in clinical background databases. Full definitions, including timeframes and codes will be provided in the Statistical Analysis Plan (SAP). [Annex 3](#) provides a summary of availability of different data types from in the participating databases. The SAP will include an elaboration on the variables available from each data partner.

### **9.3.4 Subgroups**

The feasibility of performing subgroup analyses will be strongly driven by available sample size.

In the case-cohort design a subgroup analysis will be performed in the following subgroups: young children (<12 years), adolescents (12-17 years), young adults (18-24 years), male and female.

In the cohort design of all myocarditis/pericarditis cases, a subgroup analysis will be performed in the following subgroups: Moderna vaccination targeting SARS-CoV-2-exposure status (Recently exposed, Past exposure, Never exposed), SARS-CoV-2 infection status (Recent infection, Past infection, Never infected) prior to myocarditis/pericarditis onset.

As feasible, stratified analyses by different variants of the Moderna vaccine targeting SARS-CoV-2 will be presented for both the case-cohort and the cohort designs. First, descriptive analyses in the above subgroups will be presented. Subsequent multivariable analyses will only be performed in subgroups that are sufficiently large in size. Details will be further elaborated in the SAP.

## **9.4 Data sources**

This study will be based on electronic, routinely collected data in four European countries (listed alphabetically): Denmark, Norway, Spain, and the UK. The participating databases cover the underlying countries' population fully or partially. [Table 2](#) provides an overview of the data sources in each country. Additional description of the participating data sources is provided in [Annex 3](#). Most databases and DAPs have contributed to the ACCESS protocol and are considered fit for purpose through that contribution or other previous experience in vaccine studies. The data access providers have committed to cooperate on addressing the study objectives.

**Table 2 Summary of the data sources by country**

Country	Denmark	Norway	Spain	Spain	UK
Data access partner	Aarhus University	University of Oslo	IDIAP	FISABIO	DSRU
Type of data	Record linkage	Record linkage	Record linkage & GP	Record linkage & GP	GP medical record and linked datasets
Data source name	Danish registries	Norwegian registries	SIDIAP	VID	CPRD
Size of data in 2019	5.8 M	5.4 M	5.8 M	5M	16 M
Diagnosis coding	ICD-10	ICD-10CM/ICPC	ICD-10CM	ICD-9CM/ICD-10/ICD-10CM	MEDCODE IDs/ICD-10 (for some linked datasets)
Hosp. discharge diagnoses	Yes	Yes	Yes	Yes	Yes
Intensive care unit (ICU) admission	Yes	Yes	No	Yes	Yes
Extracorporeal membrane oxygenation (ECMO) use	Maybe	Maybe	No	Yes	Yes
Date of death	Yes	Yes	Yes	Yes	Yes
Emergency unit visit diagnoses	Yes	Yes	Yes	Yes	Yes
Outpatient specialist visit diagnoses	Yes, hospital outpatient specialist clinics	Yes	Yes, referrals to specialists	Yes	Yes
Primary care diagnoses	No	Yes	Yes	Yes	Yes
COVID-testing	Routine testing only during early pandemic	Routine testing only during early pandemic	Routine testing only during early pandemic	Routine testing only during early pandemic	Routine testing only during early pandemic
Medicines dispensing outp.(pharmacy)	Yes	Yes	Yes	Yes	No
Medicines inpatient	Some	Yes, but not accurate	No	Yes	No
Medicines prescribing	No	No	Yes	Yes	Yes
COVID-19 Vaccine brand	Yes	Yes	Yes	Yes	Yes

In addition to the structured data available in these databases, medical record data will be reviewed to confirm myocarditis and pericarditis case characteristics.

In the SAP the exact variables that are required to answer all research questions will be defined, resulting in a data instance, which is a document that contains information about which data point can be found in which data source for every DAP and in which CDM table this will be stored.

The data instance is created in collaboration with the DAP. Extracting the data is done by the DAPs, following the data instance, and results in the CDM tables that contain all the data points that are required for the study.

The CDM tables are evaluated by the so-called Level-checks, which are provided by the University Medical Center Utrecht (UMCU). The Level-checks result in a quality report. The VAC4EU association coordinates this process, however, the PI is responsible for the quality of the CDM tables. After all the Level-checks have been performed and the data has been validated by the PI, the remaining part of the ETL process takes place, which results in data being submitted to a centralized platform where all results can be analysed.

## 9.5 Study size

Table 3 shows the total number of doses administered in each participating country as of April 2022.

**Table 3 Total doses of Moderna vaccination targeting SARS-CoV-2 administered in the participating countries as of April 2022**

Moderna vaccination targeting SARS-CoV-2 doses administered as of April 2022		Moderna vaccination targeting SARS-CoV-2 recipients in Data source
Denmark	1,350,690	675,345
Norway	3,293,800	1,646,900
Spain	27,721,800	SIDIAP: 1,386,090
		FISABIO: 3,107,305
UK	951,198	28,536
TOTAL:	33,317,488	6,844,176

Source: ECDC <https://vaccinetracker.ecdc.europa.eu/public/extensions/COVID-19/vaccine-tracker.html#uptake-tab> and Moderna

Considering the type of investigation, a traditional sample size calculation cannot be provided. Given that the number of cases is expected to be limited, and the number of possible risk factors for post-vaccination myocarditis (including demographic characteristics, lifestyle factors, medical history, and vaccination characteristics) under investigation, all individuals that meet the criteria for the outcome will be selected as cases, and four times as many controls will be sampled to improve statistical efficiency. This sampling will be done 1,000 times to limit biases. The number of myocarditis/pericarditis cases will drive the number of risk factors that can be investigated with adequate power in this study. The nature of this study will be observational and exploratory.

Derived from literature it is assumed that the incidence of myocarditis is approximately 0.4-4.0 per 100,000 vaccinated individuals. Based on the inclusion of subjects of the Data Access Providers (DAPs) for Denmark, Norway, Spain and UK (see Table 3), 27-274 myocarditis cases were to be expected. Similar incidence estimates were to be expected for pericarditis7, 12, . However, preliminary results suggest that 20-80 cases of myocarditis are expected for each of the DAPs, leading to an expected total study size of 100-400 myocarditis cases in the case-cohort analysis. For pericarditis, the expected number of cases is 50-140 per DAP, which corresponds to a total expected study size of 250-700.

[figure not shown]
For the myocarditis/pericarditis cohort analysis, based on preliminary outputs it is estimated that there will be approximately 40-160 cases of myocarditis studied, and 100-280 cases of pericarditis.

The estimated numbers of myocarditis and pericarditis indicate that the study should be feasible for the intended two main analyses.

## **9.6 Data management**

This study, which will be conducted based on this common protocol, will use the Vaccine monitoring Collaboration for Europe (VAC4EU, <https://vac4eu.org/>) research environment based on a common protocol, common SAP, and a common data model (CDM). The work will be conducted using a distributed network of the participating DAPs, all of whom have experience with and have contributed to the ACCESS project. The work will proceed according to Model C (Figure 4): each DAP will extract the data required for the study and transform their local patient level data into a CDM. It is proposed to use the ConcePTION CDM, which is publicly available. Extraction, transformation, and loading (ETL) design and instructions are available, as well as tools to check the quality of the data for the AESI estimated and utilised for the ACCESS background rate protocol. A common program to run quality checks, data transformation, and analysis will be prepared, verified and distributed to all DAPs. Results and summary estimates resulting from the programs will be returned to the coordinating centre for analysis and reporting. The full approach will be developed and described in the SAP.

**Figure 4 Options for multi-database studies in Europe**

## 9.7 Data analysis

Full details of the data analysis, including planned tables, figures, and listings for inclusion in the final study report will be provided in the SAP. High-level analyses and presentations are provided below.

### 9.7.1 Descriptive analyses

Attrition diagrams demonstrating the application of the inclusion and exclusion criteria will be provided. For both the case-cohort and cohort study designs, demographic characteristics of the study population and baseline characteristics will be summarised from each data source, using standard descriptive statistics. Count and percentage will be presented for categorical variables. Mean, standard deviation, median and interquartile range will be presented for continuous variables, as feasible. The number of non-missing data will be added to the summary statistics. These summary statistics will be presented for each country separately, as well as overall. Differences in baseline risks will be investigated and addressed in the statistical models as appropriate.

Country-specific counts of persons with a record of Moderna vaccination targeting SARS-CoV-2 in the datasets will be tabulated. Vaccine recipients will be described in terms of sex, age (groups), previous infection with SARS-CoV-2 and a list of relevant covariables (e.g., health care utilization, comorbidities, medicine usage and lifestyle factors), to the extent feasible for each DAP.

## 9.7.2 Main analyses

### Case-cohort analysis

For the case-cohort analysis, all cases of myocarditis and pericarditis and the full sampled control cohort will be described with respect to demographic characteristics, lifestyle factors, medical history and vaccination history. As the control cohort will be sampled 1,000 times, these variables will be described taking averages of the 1,000 samples.

Per DAP, a conditional logistic regression methodology will be applied to identify potential risk factors for development of myocarditis and pericarditis within the Moderna vaccination targeting SARS-CoV-2-exposed population (Primary objective 1). The analysis will be performed per DAP (i.e., models will be trained locally for each DAP), and results will be presented on DAP level. The parameter estimates, standard errors (SEs), and odds ratios (ORs) for each relevant model parameter will be presented together with a 95% confidence interval (CI).

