**Study design:**

The study will include two distinct designs to answer the primary and secondary objectives.

Case Cohort: To assess risk factors for development of post-vaccine myocarditis and pericarditis, a case-cohort of recipients of Moderna vaccination targeting SARS-CoV-2 will be defined in each participating database. This set will be used to investigate the first primary objective.

The Case-Cohort design requires (1) all cases of myocarditis and pericarditis who previously had received Moderna vaccination targeting SARS-CoV-2 (2) a random subsample of the original cohort ('subcohort'), selected independently of the definition of cases.

Cohort: To characterize the clinical course, outcomes, and risk factors for severe disease, a cohort of myocarditis cases (with and without prior exposure to Moderna vaccination targeting SARS-CoV-2) will be studied. Severe disease will be a composite endpoint based on the diagnosis of acute coronary syndrome, acute myocardial infarction, heart failure, atrial fibrillation/flutter, ventricular arrhythmias/cardiac arrest, pulmonary embolism or deep venous thrombosis, stroke outcomes, peripheral arterial embolism, hospital readmission, Intensive Care Unit (ICU) admission or death.

The cohort set will be used to investigate the second primary objective and both secondary objectives.

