**Figure 2 Case-cohort design**

[figure not shown]

- a. Up to a 45-day gap in medical or pharmacy enrollment allowed
- b. Risk factors may include demographic characteristics, lifestyle factors, medical history, and vaccination characteristics
- c. Earliest of: outcome of interest (myocarditis), death, end of the study period, leaving network, lost to follow-up

*\*If 2 doses within 90 days: index on first dose. If more than 90 days since last dose: re-indexing.*

*\*\* A <45 day gap for changes in insurance is not expected for European Union (EU) Data Access Providers (DAPs).*

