### 9.1.1 Moderna vaccination targeting SARS-CoV-2-exposed case-cohort

To assess risk factors for development of post-vaccine myocarditis and pericarditis, a cohort of Moderna vaccination targeting SARS-CoV-2 recipients will be defined in each participating database. This set will be used for the first primary objective.

For the case-cohort design, individuals with at least one dose of Moderna vaccination targeting SARS-CoV-2 will be used to define a cohort of Moderna vaccination recipients. Cases are those individuals who develop myocarditis or pericarditis any time during the follow-up after Moderna vaccination targeting SARS-CoV-2. The controls will be sampled from the exposed cohort, such that they align with the distribution of cases based on the month and year of documented Moderna vaccination receipt.

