### **9.2.3 Exclusion criteria**

Individuals not meeting criteria outlined in [Section 9.2.2](#) are excluded from the Moderna vaccination targeting SARS-CoV-2-exposed case-cohort and myocarditis/pericarditis cohort analyses, respectively. For the cohort design an additional exclusion criterium is applied: Persons with no record of a Moderna vaccine targeting SARS-CoV-2 but record of another vaccine for SARS-CoV-2 within 30 days prior to index date of myocarditis or pericarditis event will be excluded. Individuals who have evidence of myocarditis or pericarditis in structured data (e.g., ICD-10 codes) where review of clinical data is not performed due to sampling, or is incompatible with adjudication criteria according to the Brighton Collaboration Case Definition for myocarditis or pericarditis will be described but will not be included as cases in primary analyses. In the Moderna vaccination targeting SARS-CoV-2-exposed case-cohort design, non-confirmed myocarditis/pericarditis cases will be censored at the onset of the false positive myocarditis/pericarditis diagnosis.

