**Table 1 Study objectives and endpoints**

Objective	Endpoint	Analysis Set
Primary		
To identify possible risk factors for myocarditis and pericarditis post-Moderna vaccination targeting SARS-CoV-2, including demographic characteristics, medical history, and vaccination characteristics.	Myocarditis or pericarditis within 30 days after Moderna vaccination targeting SARS-CoV-2.	Case-cohort
To characterize the clinical course of myocarditis and pericarditis of varying origin, including myocarditis and pericarditis associated with Moderna vaccination targeting SARS-CoV-2, and myocarditis or pericarditis not associated with vaccinations targeting SARS-CoV-2, and to identify prognostic factors in the course of myocarditis and pericarditis.	Clinical outcomes within 30 days of myocarditis' or pericarditis' onset: 
 
• Acute coronary syndrome or acute myocardial infarction;
 
• Heart failure;
 
• Atrial fibrillation/flutter;
 
• Ventricular arrhythmias/cardiac arrest;
 
• Pulmonary embolism or deep venous thrombosis;
 
	Cohort

	
 
• Stroke outcomes;
 
• Peripheral arterial embolism;
 
• Hospital readmission;
 
• ICU admission; and/or
 
• Death.
 
 
Long term outcome (e.g., 90 day, 6 months or 12 months depending on availability of data):
 
 
• Acute coronary syndrome or acute myocardial infarction;
 
• Heart failure;
 
• Atrial fibrillation/flutter;
 
• Ventricular arrhythmias/cardiac arrest;
 
• Pulmonary embolism or deep venous thrombosis;
 
• Stroke outcomes;
 
• Peripheral arterial embolism;
 
• Hospital readmission;
 
• ICU admission; and/or.
 
• Death.
 
	

Secondary
		

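### Case-cohort: follow-up rules do not act on the controls' time at risk, so if cases count at any time after vaccination, odds ratios for high-exit groups fall below the rate ratio

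*Protocol*

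**What the plan says.** **Follow-up.** Figure 2, note c, ends follow-up at the "Earliest of: outcome of interest (myocarditis), death, end of the study period, leaving network, lost to follow-up". Section 9.2.3 adds that in the case-cohort "non-confirmed myocarditis/pericarditis cases will be censored at the onset of the false positive myocarditis/pericarditis diagnosis". Both are person-time rules.

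**Controls.** The abstract (Study design) defines the comparison group as "a random subsample of the original cohort ('subcohort'), selected independently of the definition of cases". Section 9.1.1 says: "The controls will be sampled from the exposed cohort, such that they align with the distribution of cases based on the month and year" of vaccination. Section 9.5 sets four controls per case and repeats the sampling 1,000 times. No section requires a control to be under observation and event-free at the case's time since vaccination.

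**Analysis.** For Primary objective 1, section 9.7.2 states that "a conditional logistic regression methodology will be applied to identify potential risk factors for development of myocarditis and pericarditis". It is fitted separately in each data source and reported as odds ratios.

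**Case window.** Table 1 gives the endpoint as "Myocarditis or pericarditis within 30 days after Moderna vaccination targeting SARS-CoV-2". Section 9.1.1 says: "Cases are those individuals who develop myocarditis or pericarditis any time during the follow-up after Moderna vaccination targeting SARS-CoV-2".

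**The concern.** A random subsample taken at the start, censoring rules that run on person-time, and a logistic model that takes no follow-up time do not fit together. A recipient who dies or leaves soon after the dose had little time in which to become a case. Under the stated sampling that person is drawn as a control with the same probability as someone observed to the end, and then carries full weight. Groups that die or leave early are therefore over-counted among controls relative to their time at risk, and their odds ratios fall below the rate ratio.

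Section 9.3.3 lists several candidate factors that could mark such groups: age, cancer history, chemotherapy, chronic kidney disease, immunocompromise. Section 9.1 says that the case-cohort may help to identify people without increased risk, so for this purpose a downward shift is the unhelpful direction.

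**Working it through.** **The plan's own figure.** The five data sources in Table 3 sum to 675,345 + 1,646,900 + 1,386,090 + 3,107,305 + 28,536 = 6,844,176 recipients. Multiplied by 0.4 and 4.0 per 100,000 this gives 27.4 and 273.8, which reproduces the 27-274 of section 9.5. That section gives no effect size, exit rate or mean follow-up, so the bias cannot be derived from the protocol alone.

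**Inputs.**
- Short window: 30 days (Table 1).
- Long window: 6 January 2021 to 31 August 2024 (section 9.2.1), which is 3.65 years at most.
- Yearly exit rates by death or leaving: assumptions, shown as a range.

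**Formula.** For a rare outcome with constant hazard and controls drawn at baseline,

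OR / rate ratio = m(high-exit group) / m(reference group), with m = (1 − exp(−μt)) / μ,

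where μ is the yearly exit rate and t the window in years.

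Example with μ = 0.20 against 0.01 and t = 3.65: (1 − exp(−0.73)) / 0.20 = 2.59 years, and (1 − exp(−0.0365)) / 0.01 = 3.58 years. The ratio is 2.59 / 3.58 = 0.72.

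| Assumed exit per year | 30 days | 1 year | 3.65 years |
|---|---|---|---|
| 0.05 vs 0.01 | 0.998 | 0.98 | 0.93 |
| 0.10 vs 0.01 | 0.996 | 0.96 | 0.85 |
| 0.20 vs 0.01 | 0.992 | 0.91 | 0.72 |
| 0.50 vs 0.02 (extreme) | 0.981 | 0.79 | 0.48 |

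**Check by simulation.** Settings: 10% of recipients in the high-exit group, true hazard ratio 1.5, exit 0.20 against 0.01 per year, about 400 cases, four controls per case, 20 repeats.

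| Window | Controls drawn at baseline | Controls at risk at the case's time |
|---|---|---|
| 30 days | 1.55 | 1.55 |
| 3.65 years | 1.04 | 1.51 |

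The formula predicts 1.5 × 0.72 = 1.08 for baseline controls at 3.65 years. The simulated 1.04 agrees within its error: the SD of the log odds ratio was 0.124, so the standard error over 20 repeats is 0.124 / √20 = 0.028.

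**Does conditioning help?** Section 9.7.2 does not say how the matched sets are formed. If they are the months of vaccination, conditioning equalises the end of the study period within a set. It does not equalise death or leaving, which is where the groups differ.

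**Clustering of cases.** Section 7 reports that most post-vaccination cases occurred within 14 days. If half the cases fell within 30 days (an assumption), the 3.65-year factors would be roughly 0.5 × 0.998 + 0.5 × 0.93 = 0.96, 0.5 × 0.996 + 0.5 × 0.85 = 0.92, and 0.5 × 0.992 + 0.5 × 0.72 = 0.86.

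**The case against.** The strongest reply is that the tabulated endpoint is 30 days, in both the abstract and Table 1, and that section 9.3.2 reviews records of diagnoses within 30 days of exposure. At 30 days the shift is 0.2% to 2%. The simulated SE of the log odds ratio is about 0.15 with some 400 cases, and a single data source, where the models are fitted, expects only 20-80 myocarditis cases. On that window the point has no practical effect on the estimates. This stands. It does not dispose of the point, because section 9.1.1 says otherwise, note c has no 30-day stop, and section 9.3.1 classes case-cohort cases more than 30 days after a dose as past exposure.

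The long-window factors are also upper-end. They assume constant hazard and the maximum follow-up for everyone, whereas Figure 2 re-indexes on doses more than 90 days after the last. They are crude, and adjustment for age may absorb part of the differential exit. The exit rates have no source in the protocol. All of this stands.

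Finally, conditional logistic regression is the standard analysis for controls sampled from risk sets, and the SAP may specify such sampling. That the controls need not be at risk is inferred from the protocol's silence together with the random-subsample wording. But the protocol is not merely silent: a subcohort chosen independently of case status is a different scheme, so a SAP with risk-set sampling would depart from it.

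A reader might infer that the follow-up rules have no effect at all. They do not support that: events after leaving, after study end or after a censored false positive can still be excluded as cases. Censoring at a false positive should in any case concern few people.

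**Conclusion.** The point holds in a conditional form. The stated sampling and model leave the follow-up and censoring rules without any action on the controls' time at risk, and the resulting shift for high-exit groups is downward. It is about 7%, 15% or 28% for assumed exit of 5%, 10% or 20% a year against 1% over 3.65 years, with constant hazard and maximum follow-up, and less if cases cluster soon after vaccination. Under the 30-day endpoint it is about 2% or less.

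A reader might conclude that odds ratios for frail groups are biased downward in any event, or that true risk factors will appear protective. The documents do not support either. The first fails at 30 days. The second needs high exit rates over the full period, which the protocol neither states nor implies.

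The design text should still be reconciled. The two windows separate a negligible bias from a material one, and a material one would not shrink with more cases.

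**What to change.** 1. State one case window, in the same terms, in section 9.1.1, Figure 2 (including note c) and Table 1.
2. In sections 9.1.1, 9.5 and 9.7.2, sample the four controls per case from recipients with the same month and year of index dose who are alive, enrolled, uncensored and event-free at the case's number of days since index dose. Keep conditional logistic regression on these matched sets. The odds ratio then estimates the rate ratio, and note c and the censoring rule in 9.2.3 act on controls as well as cases. Change the random-subsample wording in the abstract's design summary to match.
3. Alternatively, keep the baseline subcohort and analyse it with a weighted Cox model, which uses the follow-up time directly.

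Cost: the sampling program, including the 1,000-fold repetition, and the design wording must change, since option 2 turns the design into a nested case-control study. The dates of vaccination, diagnosis, death and enrolment are already needed for the existing rules, so no new data are required. If the window is settled at 30 days, the change costs nothing in validity and simply makes the text consistent.
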